Conjunctival hyperemia is a common adverse reaction of PGAs, mainly due to vasodilation in sclera and conjunctiva. [37] Several studies place the occurrence of conjunctival hyperemia between 27% and 49%. [32, 38, 39]

Other reactions commonly attributed to PGAs are the growth and darkening of the eyelashes and the darkening of the iris. [40, 41, 42]

There have been some reports of cases of potential risk of cystoid macular edema in pseudophakic patients using PGAs. [43, 44] Nevertheless, this relationship has not been confirmed with appropriate scientific literature. [37]

Cases of anterior uveitis related to the use of travoprost have been reported, which remit when the travoprost is discontinued and with the administration of topical steroids. [45]

5.2.4 Risk benefit evaluation.

5.2.4.1 Known potential risks.

The frame of reference of travoprost places it as a safe molecule, with a known safety and tolerability profile. PRO-179 shares the same active principle, in the same concentration as Travatan®. The main adverse effects, such as conjunctival hyperemia and alterations in eyelashes and eyelids are reversible. The effects on changes in iris coloring appear in the first 6 to 8 months of treatment.

Pre-clinical studies of PRO-179 compared to Travatan® have been conducted, where a safety and toxicity profile has been demonstrated, as well as similar bioavailability in a model of albino rabbits New Zealand. [46, 47]

5.2.4.2 Known potential benefits.

The effectiveness of travoprost has been previously documented in the literature. Generic drugs help reduce the costs of treatments by generating direct competition with the innovator.

The present study does not represent a direct benefit for patients; nevertheless, neither a potential risk in the medium or long term; due to the antecedents that place travoprost as safe. In the same way, the procedures proposed to be carried out during the study do not represent an additional risk to the subject.

5.3 Statement of the problem.

Chronic diseases, such as glaucoma, pose a significant economic burden to the patient and society. Due to this the health authorities support the development of generic medicines, once the patent of the innovator has expired. The above would mean obtaining the drugs at a lower cost.

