At the counting stage, the participant number will be assigned consecutively, using 3 consecutive digits. Once the subject has been selected, he will be assigned a number with which he will be identified throughout the study. Said code will be composed of eight numbers in the following order from left to right:

- three digits of the molecule under study according to the denomination by the sponsor.
- two digits corresponding to the research center number.

- three digits of the number consecutive to its inclusion assigned to the research center.

Example:

6.3 Intervention.

The subjects will be divided into two equal groups, to which they will be assigned randomly and blinded to one of the products in research (PI) PRO-179 or Travatan®.

Dosage: 1 drop every 24 hours, at night, in both eyes.

Instructions for administration: instillate a drop in the conjunctival sac, it is recommended to exert gentle traction on the lower eyelid, with the index finger, to expose the cul-de-sac and instillation. Avoid blinking energetically for the next few minutes or closing your eyes in a forced way.

Duration of the intervention: 10 days.

6.3.1 Medications administered.

6.3.1.1 Drug under study.

- Generic name: Travoprost
- Distinctive denomination: Bristrio® (PRO-179)
- Active principles: Travoprost 0.004%.
- Pharmaceutical form: Ophthalmic solution
- Presentation: multi-dose dropper bottle, 2.5 ml.
- Prepared by: Sophia Laboratories, S.A. of C.V.
- Description of the solution: transparent solution, free of visible particles.
- Description of container: White bottle with 5mL capacity, made of low density polyethylene.

Agent	Quantity mg / mL	Function
Travoprost	0.040	Active principle
Hydroxypropylbetacyclodextrins	Not showing	Stabilizer
Mannitol	Not showing	Toning
Boric acid	Not showing	Buffer Agent
Sodium Borate Dehydrated	Not showing	Buffer Agent
Disodium edetate Dihydrate	Not showing	Chelating Agent
Benzalkonium Chloride (1)	Not showing	Conservative
Water for the preparation of Injectables c.b.p.	1.000 mL	Vehicle

Table 2. Quali-quantitative formulation of PRO-179

6.3.1.1 Reference medicine.

- Generic name: Travoprost
- Distinctive denomination: Travatan®
- Active ingredients: Travoprost 0.004%
- Pharmaceutical form: Ophthalmic solution.
- Presentation: multi-dose dropper bottle, 2.5 ml.
- Prepared by: Alcon Laboratories Inc.
- Description of the solution: transparent solution, free of visible particles.
- Consult information to prescribe.

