- Adverse events: see 6.4.3.5 Presence of adverse events.
- Review of laboratory tests: see Baseline visit.

6.5.1.6 Early termination visit.

If the research subject's participation ends earlier than scheduled, due to an adverse event or any other situation, an unscheduled visit will be made, which will serve as the final visit. In case the subject refuses to attend, the last visit made will be taken as final. Subsequently, the security call will be made in the normal time established.

6.5.2 Diagram of the study.

[figure not shown]
[figure not shown]

Figure 3. Horizontal diagram of the study.

* Baseline measurements can be taken from those made during the screening visit. It is the investigator's prerogative to perform them again at the baseline visit.

Figure 4. Vertical diagram of the study.

6.6 Sample size.

A total size of 24 subjects is estimated, divided into 2 intervention groups (12 subjects per group). A 45-day enrollment time is expected for the total sample.

6.6.1 Calculation of the sample size.

Although there are no references on the calculation of sample size in phase I studies, the incidence of ocular adverse events was considered, basing the calculation on the presence of conjunctival hyperemia.

Based on the following work hypothesis:

$$H_0 = p_A - p_B \leq \delta$$

$$H_1 = p_A - p_B > \delta$$

The formula for proportions was used (Chow et al., 2008) [62]:

$$n_B = \left(\frac{p_A(1-p_A)}{k} + p_B(1-p_B) \right) \left(\frac{z_{1-\alpha} + z_{1-\beta}}{p_A - p_B - \delta} \right)^2$$

The study by Mishra et al, whose objective was to compare the efficacy and safety of latanoprost, bimatoprost, travoprost and timolol in the reduction of intraocular pressure (IOP) and the incidence of adverse events in patients with primary angle glaucoma, was used as a reference open (GPA). [63] This was a prospective, unicentric study in 140 patients with recent diagnosis of POAG who were assigned to some intervention (n = 35 per arm / both eyes). Follow-up at 2, 6 and 12 weeks. The main safety variable was the presence of adverse events (AD). OAEs were observed in 41.9% (13/31) of patients treated with travoprost with an incidence of conjunctival hyperemia of 12.9%. The EA reported were: conjunctival hyperemia, dry eye, discomfort and keratitis.

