Calculation: the percentage of AD presented in the group treated with travoprost was considered. Expecting a similar proportion of conjunctival hyperemia due to PGA and healthy subjects. Considering a power of 80%, a significance level of 0.05 (α) and a non-inferiority margin of 5% (δ).

Calculated sample: 20, increasing the calculation by 20% considering possible losses, 25 subjects.

Suggested sample: 12 subjects (24 eyes) per treatment arm.

6.7 Recruitment.

It is essential that, if necessary during the development of this research protocol, the principal investigator requests the approval of the Research Ethics Committee and the Research Committee, as well as the authorization of COFEPRIS, to publish or disseminate in mass media, the invitation to participate in the study to those people who meet the selection criteria.

It is possible to discuss with other health professionals the opportunity for healthy subjects to be evaluated by an ophthalmologist at no cost, as well as cabinet exams that will allow the more accurate determination of their ocular clinical status by participating in a sponsored clinical research protocol by Sophia Laboratories, SA of C.V.

7 Methods. Assignment of the intervention.

7.1 Generation of the allocation sequence.

Two strata corresponding to the intervention groups will be used, which will be balanced for a research center. The allocation will be 1: 1. The generation will be carried out by a third party, authorized by Sophia Laboratories, S.A. of C.V., through its electronic system. The information corresponding to this third party will be found in the file.

7.2 Blinding mechanism.

Blinding will be done by the Department of Clinical Operations of Sophia Laboratories, S.A. of C.V. Which will consist of the elimination of the primary label (commercial) in the case of Travatan® and the placement of a label identical to the other IP. Because the bottle in which Travatan® is packaged differs in color and shape to that used for PRO-179, a masking will be made in the primary packaging which will be identical for the interventions. The subject will have determinedly prohibited to comment with another person that is not the pharmacist aspects related to the primary container (bottle).

7.3 Implementation.

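### Section 6.6.1 borrows event rates from glaucoma patients followed to 12 weeks for a trial with 10 days of drops in healthy subjects, and no rate in the documents supports the stated 80% power

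*Combined protocol and SAP*

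**What the plan says.** Section 6.6.1 describes its approach as "basing the calculation on the presence of conjunctival hyperemia". Its only source is a study in "140 patients with recent diagnosis of POAG who were assigned to some intervention", with "Follow-up at 2, 6 and 12 weeks". From the travoprost arm it reports: "OAEs were observed in 41.9% (13/31) of patients treated with travoprost with an incidence of conjunctival hyperemia of 12.9" per cent. For the calculation, it says that "the percentage of AD presented in the group treated with travoprost was considered", and it bridges to this trial with one sentence: "Expecting a similar proportion of conjunctival hyperemia due to PGA and healthy subjects". It then states 80% power, a significance level of 0.05 and a non-inferiority margin of 5%. The result is a calculated sample of 20, raised to 25 for losses, and an adopted sample of 12 subjects (24 eyes) per arm. The values of pA and pB are never stated.

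Section 6.3 gives the exposure in this trial: "Duration of the intervention: 10 days". The synopsis and section 6.4.4 place the adverse-event checks at days 5, 11 and 14. Section 5.2.3, on the safety of travoprost, says: "Several studies place the occurrence of conjunctival hyperemia between 27% and 49" per cent. Section 6.6.1 does not mention that range.

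**The concern.** The number of events that can occur in this trial's own window determines what the primary adverse-event comparison can show. The rates in 6.6.1 come from a different population with a much longer follow-up. The bridging sentence deals with population, without giving support, and does not deal with duration. The hyperemia rate also lies below the range the protocol itself reports two chapters earlier. A shorter exposure could lower the expected rate and the range in 5.2.3 would raise it; 6.6.1 discusses neither.

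This matters because section 8.3.1 will call the product safe and tolerable if no clinical and statistical differences appear in the primary variables. Under that rule, few events or few subjects favour a positive conclusion. The 80% power statement is what would give weight to a finding of no difference. If the design does not have that power, a null result says little about similarity, yet the report could still cite the calculation.

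**Working it through.** **Inputs.** Any ocular adverse event 41.9% (13/31); hyperemia 12.9% (4/31 = 0.129); hyperemia range 27–49% (section 5.2.3); margin 0.05; power 80%; allocation 1:1. The printed formula uses z(1−α), so α = 0.05 is one-sided. z(0.95) + z(0.80) = 1.645 + 0.842 = 2.486, and its square is 6.183.

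**Reproducing the printed 20.** The formula is n = [pA(1−pA) + pB(1−pB)] × [2.486 / (pA − pB − δ)]². With pA = 0.129, pB = 0.419 and δ = 0.05:

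(0.1124 + 0.2434) × 6.183 / (−0.34)² = 19.03, rounded up to 20; and 20 / 0.8 = 25.

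Of the substitutions tried, only this one returns 20. With the opposite sign of δ it gives 38.2; with a two-sided α it gives 24.2. The pair 12.9% and 41.9% is two different events in the same travoprost arm, not the rates of two treatments, and it does not match the stated similar proportion.

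**With the stated similar proportions.** When pA = pB = p, the formula becomes n = 2p(1−p) × 6.183 / 0.05². Approximate power with N per arm is Φ(0.05 / √(2p(1−p)/N) − 1.645).

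| Rate p | n per arm for 80% | Power, 12 subjects per arm | Power, 24 eyes per arm taken as independent |
|---|---|---|---|
| 12.9% | 555.7 | 10.0% | 13.0% |
| 27% | 974.9 | 8.6% | 10.5% |
| 41.9% | 1,204.1 | 8.1% | 9.8% |
| 49% | 1,236.0 | 8.1% | 9.7% |

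**If the rate is lower because exposure is short.** The documents give no 10- or 14-day rate. As an assumption only, take a constant hazard over 84 days: p(t) = 1 − (1 − p₈₄)^(t/84).

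| Event | Day | p(t) | n per arm for 80% | Power, 12 subjects per arm |
|---|---|---|---|---|
| Hyperemia | 10 | 1.6% | 79.3 | 24.9% |
| Hyperemia | 14 | 2.3% | 110.0 | 20.5% |
| Any event | 10 | 6.3% | 290.2 | 12.7% |
| Any event | 14 | 8.7% | 390.9 | 11.3% |

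Expected subjects with any event per arm of 12 would be 12 × 0.063 = 0.75 to 12 × 0.087 = 1.0, against 12 × 0.419 = 5.0 at the source rate. The chance of no hyperemia in all 24 subjects would be (1 − 0.0163)²⁴ = 67% or (1 − 0.0228)²⁴ = 58%. With counts this low the normal approximation is rough, and the power figures are indicative.

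**What 12 per arm can show.** With 0 of 12 affected, the one-sided 95% upper limit is 1 − 0.05^(1/12) = 22%. Fisher's two-sided test of 0/12 against 4/12 gives p = 0.093, and against 5/12 gives p = 0.037.

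**How far apart 12.9% and 27–49% are.** The exact 95% interval for 4/31 is 3.6–29.8%, which just reaches the lower end of the range in 5.2.3.

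**The case against.** A sponsor could fairly reply as follows.

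- *The rates may not be 12-week rates.* A reader might infer that 41.9% and 12.9% accumulated over 12 weeks. Section 6.6.1 lists visits at 2, 6 and 12 weeks and does not date the rates. The 2-week visit is close to this trial's day-14 call, and 5.2.3 attributes hyperemia to vasodilation, which gives no reason to expect even accrual over 84 days. This stands. The constant-hazard values are a sensitivity case, and the day-14 values also continue the hazard after the drops have stopped.
- *12.9% does not contradict 27–49%.* A reader might infer a contradiction. The interval for 4/31 reaches 27%, and the sentence before the range in 5.2.3 speaks of prostaglandin analogues as a class. That range comes without a duration, and the titles of its sources concern glaucoma or ocular hypertension, so it is no better as a 10-day rate in healthy subjects. The supportable statement is that the two figures are not reconciled.
- *Short exposure does not cause the loss of power.* A reader might infer that time scaling takes the power from about 82% at n = 20 to 47–48%. Those figures need 12.9% and 41.9%, or their scaled values, to be the rates of the two arms, which they are not. Under the similar proportions that 6.6.1 states, scaling raises power, for hyperemia from about 10% to 21–25% with 12 per arm. The same mixed pairing with 49% hyperemia is incoherent, since hyperemia is one of the ocular events counted in the 41.9%.
- *The arithmetic reproduces, and 24 subjects is a reasonable size for a phase I trial.* Both are true. The complaint is about the input and the power claim, not the size.

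None of these replies supplies a rate at which the planned sample has 80% power.

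**Conclusion.** The point holds in a limited form. Section 6.6.1 uses rates from glaucoma patients followed to 12 weeks, without addressing the 10-day exposure and without reconciling 12.9% with section 5.2.3. No rate in the documents gives the stated power. Under similar proportions, a 5% margin and one-sided 0.05, power is about 8–10% with 12 subjects per arm and about 10–13% with 24 eyes treated as independent. A lower rate from short exposure helps only a little: about 11–25% with 12 subjects per arm, and that rests on the constant-hazard assumption.

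The rate source is not the largest fault in the calculation. Even at 12.9%, the stated assumptions need about 556 per arm, and the printed 20 depends on contrasting two events from one arm. Correcting that would still leave an event rate with no stated basis for this trial's window. The documents do not show what the true 10–14 day rate is, so the conclusion is that the power claim is unsupported, not that a particular rate should replace the one used. The change should be made, but it does not call the trial's size or conduct into question.

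**What to change.** In 6.6.1:

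- Describe 41.9% and 12.9% as rates from glaucoma patients followed to 12 weeks, and note the 27–49% in 5.2.3 beside them.
- State that no rate for 10–14 days in healthy subjects is available. Label any time-scaled value as a sensitivity assumption, not as the expected rate.
- Withdraw the 80% power statement and keep 24 subjects.
- State the precision of 12 per arm instead: the 22% upper limit after 0/12, and the need for at least 5/12 against 0/12 before Fisher's test falls below 0.05.

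In 8.3.1:

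- Report the between-arm difference in subjects with an adverse event with an exact 95% interval.
- State that similarity will not be concluded from a non-significant test alone.

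The cost is some rewording and one added interval. No subjects, visits or procedures are added. The downside is that the protocol can no longer cite a favourable power figure.

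### Section 6.6.1 claims 80% power for a 5-point non-inferiority margin; with equal rates in the two arms, 12 subjects per arm give about 8–10%

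*Combined protocol and SAP*

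**What the plan says.** Section 6.6 fixes the size: "A total size of 24 subjects is estimated, divided into 2 intervention groups (12 subjects per group". Section 6.6.1 describes "basing the calculation on the presence of conjunctival hyperemia" and prints a sample-size formula for two proportions using z at 1−α, that is, one-sided. The printed hypotheses are H0: pA − pB ≤ δ and H1: pA − pB > δ.

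The rates cited come from the travoprost arm of one earlier study in glaucoma patients: "OAEs were observed in 41.9% (13/31) of patients treated with travoprost with an incidence of conjunctival hyperemia of 12.9"%. The text continues "Expecting a similar proportion of conjunctival hyperemia due to PGA and healthy subjects", and then "Considering a power of 80%, a significance level of 0.05 (α) and a non-inferiority margin of 5% (δ". The result is "Calculated sample: 20, increasing the calculation by 20% considering possible losses, 25 subjects", followed by "Suggested sample: 12 subjects (24 eyes) per treatment arm".

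The section does not give pA or pB, does not say which product is A, and does not say whether 20 and 25 are totals or per arm.

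Three other places bear on this:

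- Section 5.2.3 gives a higher hyperemia range: "Several studies place the occurrence of conjunctival hyperemia between 27% and 49"%.
- Section 5.5.4 makes similarity of the two products the study hypothesis.
- Section 8.3.1 and Table 3 (section 6.4.3) plan only tests of difference for the primary variables: chi-square or Fisher for adverse-event presence, Mann-Whitney U for event counts and the ICO score. Section 8.3.1 then treats the product as safe and tolerable if no clinical and statistical differences appear in any primary variable.

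**The concern.** A 5-point margin on an incidence somewhere between 13% and 49% normally needs hundreds of subjects per arm, so 80% power from 12 per arm is implausible on its face. Two things are at stake.

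First, a reader who trusts the 80% will take a null result as evidence that the products are alike.

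Second, the conclusion rule in 8.3.1 favours a small sample. No clinical difference is defined for adverse events or for the ICO score, so the only part of the rule that can be applied as written is statistical non-significance. The smaller the trial, the more likely it is to pass, whatever the true difference.

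**Working it through.** **Inputs.** From 6.6.1: α = 0.05 one-sided (z = 1.645), power 80% (z = 0.842), δ = 0.05, 12 subjects (24 eyes) per arm, rates 12.9% (hyperemia) and 41.9% (any ocular adverse event). From 7.1: 1:1 allocation, so k = 1. From 5.2.3: 27%, the low end of the plan's own hyperemia range. Assumption: similar means pA = pB.

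**Step 1: reproduce the stated 20.** The formula is

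n_B = [pA(1−pA) + pB(1−pB)] × [(1.645 + 0.842)/(pA − pB − 0.05)]².

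Equal rates do not come near 20 (step 2). Among the rates the plan cites, I matched it only by putting the two different outcomes into the two arms. With pA = 0.129 and pB = 0.419, the variance term is 0.1124 + 0.2434 = 0.3558 and the denominator is −0.34. This gives n_B = 19.03, rounded up to 20, and 20/0.8 = 25, as printed. The reverse order gives 38.19, or 39. That these inputs were used is my inference. They mix hyperemia and any ocular event from a single travoprost arm, and they imply a 29-point difference between the products.

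**Step 2: the formula with equal rates.** Here ((1.645 + 0.842)/0.05)² = 2,473.0 (unrounded z-values), multiplied by 2p(1−p). Power for non-inferiority is Φ(0.05/SE − 1.645), with SE = √(2p(1−p)/n).

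| Common rate | 2p(1−p) | n per arm for 80% | SE, n = 12 | Power, 12 subjects | Power, 24 eyes as independent |
|---|---|---|---|---|---|
| 12.9% | 0.2247 | 555.7 → 556 | 0.137 | 10.0% | 13.0% |
| 27% | 0.3942 | 974.9 → 975 | 0.181 | 8.6% | 10.5% |
| 41.9% | 0.4869 | 1,204.1 → 1,205 | 0.201 | 8.1% | 9.8% |

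The normal approximation is rough at this size. Exact binomial enumeration with 12 per arm, requiring the upper one-sided 95% limit to fall below 5 points, gives these powers with Agresti-Caffo and Wald limits respectively: 6% and 21% at 12.9%, 8% and 11% at 27%, 8% and 9% at 41.9%. With 12 per arm, 80% power would need a margin of 2.486 × SE: 34 points at 12.9% and 50 points at 41.9%.

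**Step 3: power on the inferred inputs.** With pA = 0.129 and pB = 0.419, SE = √(0.3558/12) = 0.172 and Φ(0.34/0.172 − 1.645) = 63%. With 24 independent eyes, SE = 0.122 and the power is 87%.

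**Step 4: direction of H1.** If A is the test product, H1 as printed says its event rate exceeds the reference rate by more than 5 points, which is not non-inferiority. Because the formula squares the difference, it does not show this. The powers in step 2 are for the correct direction (pA − pB < δ). For H1 as printed, equal rates give 2–3%.

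**Step 5: the test the plan does run.** Exact enumeration of two-sided p ≤ 0.05 when the true rates are 41.9% and 12.9%:

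| Per arm | Fisher: power / missed | Uncorrected Pearson: power / missed |
|---|---|---|
| 12 subjects | 21% / 79% | 35% / 65% |
| 10 subjects (12 less 20% = 9.6) | 13% / 87% | 26% / 74% |
| 24 eyes as independent | 53% / 47% | 64% / 36% |

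Against 1/12, significance needs 7/12 with Fisher (p = 0.027; 6/12 gives 0.069) or 6/12 with Pearson (p = 0.025; 5/12 gives 0.059).

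**The case against.** **Phase I trials are rarely powered.** Section 6.6.1 itself says it found no references for sizing them, and 5.6.1 justifies a small, short study. That is a fair reason to keep 12 per arm. It is not a reason to attach 80% power and a margin to that number.

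**Equal rates are not stated.** Read literally, the sentence about a similar proportion carries the patient rate over to healthy subjects; it does not set PRO-179 equal to Travatan. This stands as a point of wording, and equality remains my assumption. It is the usual design assumption for non-inferiority and fits the hypothesis in 5.5.4. The only alternative that yields 20 contradicts that hypothesis and still gives just 63% with 12 subjects.

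**The unit may be the eye.** The sequence 20 eyes per arm, 25 with losses, then 24 eyes in 12 subjects hangs together, and 8.3.1 counts adverse events in eyes. On the mixed inputs that gives 87%. Against it, the plan labels the 25 as subjects, a person's two eyes are not independent, and a 29-point difference is still required. This reading may explain the number; with equal rates it still gives at most 13% power.

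**The 8–10% is approximate.** This stands: at 12.9%, with about 12 × 0.129 = 1.5 events expected per arm, the exact figure runs from 6% to 21% depending on the interval method. Every value is far below 80%.

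**Conclusion.** The concern holds. The plan does not have the power it states: with equal rates it has about 8–10% with 12 subjects per arm (6–21% across the exact calculations), and 10–13% even if all eyes are treated as independent. The required size is 556 to 1,205 per arm. This rests on equal true rates, a one-sided α of 0.05 as in the printed formula, and rates taken from the plan itself.

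The stated 80% also describes a test that is not planned, since nothing in 8.3.1 or Table 3 refers to the 5-point margin. The most serious consequence is the conclusion rule: non-significance would be read as similarity when a 29-point difference would be missed in roughly two-thirds to four-fifths of trials of this size. This needs to be corrected before the analysis.

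**What to change.** **In 6.6.1**, remove the power and margin statement and the H0/H1 pair. Keep 12 subjects per arm, and say that this size is not supported by a power calculation and that no non-inferiority claim at 5% will be made. State the precision instead:

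- Approximate 95% half-width for the difference in incidence, 1.96 × √(2p(1−p)/n): ±27, ±36 and ±39 points at 12.9%, 27% and 41.9% with 12 per arm; ±29, ±39 and ±43 if losses leave 10.
- Because few events are expected, Newcombe examples: ±31 points for 2/12 versus 2/12 and ±35 for 5/12 versus 5/12.
- For the ICO score the plan gives no SD, so use SD units: t(0.975, 2n−2) × √(2/n) = ±0.85 SD with 12 per arm and ±0.94 SD with 10. This is a guide based on a mean difference with equal SDs.

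**In 8.3.1**, report adverse-event incidence per subject, with eye counts as an additional listing. Give the between-arm difference with a 95% confidence interval for incidence (Newcombe, for example) and for the ICO score (a Hodges-Lehmann shift goes with the planned Mann-Whitney test). Define the clinical difference for each before unblinding, and base any statement of similar safety and tolerability on those intervals, not on a p-value above 0.05.

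**Cost.** Protocol and analysis wording only; enrolment does not change. The price is a less favourable design statement and a more cautious conclusion: with intervals this wide, the trial may be able to describe similarity but not to declare it.
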